Height and weight		X			X	Section 8.4.3; height should be measured with a stadiometer.
Vital signs	X	X	X	X	X	Section 8.4.3; vital signs are taken before blood sampling and other procedures.
Efficacy assessments						
Evaluate %BSA affected by AD (excluding skin dryness)	X	X	X	X	X*	
Section 8.2.2; evaluate %BSA (excluding the scalp) affected by active AD lesions using the handprint method.
 
*At Week 8, the %BSA range is 0% to ≤ 20% for the LTS period.

Target lesion identification	X	X*				
Section 8.2.3; the longest diameter and the span perpendicular to the longest diameter will be measured in centimeters.
 
*For photography participants, a lesion of ≥ 5 cm² (target lesion) is to be identified at screening and confirmed at the baseline visit (excluding the hands, feet, and genitalia).

Photography (target lesion and regional body area)*		X	X	X	X	
Section 8.2.4; photography of the target lesion area identified at Day 1/baseline even if the lesion has cleared.
 
*Performed only for photography participants at selected sites.

IGA	X	X	X	X	X*	
Section 8.2.5.
 
*At Week 8, the IGA range is 0 to 4 for the LTS period.

EASI	X	X	X	X	X	Section 8.2.6; evaluate EASI in 4 regions (head/neck, upper limbs, trunk, and lower limbs) and overall.
Itch NRS	eDiary is completed each evening from screening through the last application of study cream during the VC period (night prior to Week 8 visit).				
Section 8.2.7; baseline itch (defined as the average of at least 4 of the 7 days directly before Day 1) must be NRS ≥ 4.
 
Note: Itch is collected from participants ≥ 6 years of age.
	

Table 3: Schedule of Activities: Vehicle-Controlled Period (Continued)

Visit Day (Range)	Screening	VC Period				Notes and Protocol Section	
	Days -28 (+ 7 ^a) to -1	Day 1/ Baseline	Wk 2 (± 3 d)	Wk 4 (± 3 d)	Wk 8 ^b /ET (± 3 d)		
Laboratory assessments					Blood draws for clinical laboratory tests must be performed before the in-clinic study cream application. Use of a topical anesthetic prior to blood draw is recommended.		
Serum chemistries	X	X*	X		X	Section 8.4.4. *Day 1 testing will be performed only if the interval between this visit and the screening visit is > 2 weeks.	
Hematology	X	X*	X		X	Section 8.4.4. *Day 1 testing will be performed only if the interval between this visit and the screening visit is > 2 weeks.	
Serology	X*					Section 8.4.4.3. *HIV antibody.	

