5.1. Inclusion Criteria

Participants are eligible to be included in the study only if all of the following criteria apply:

1. Male and female children aged ≥ 2 years to < 12 years (at the screening visit).
2. Diagnosis of AD as defined by the Hanifin and Rajka (1980) criteria.
3. AD duration of at least 3 months (participant/parent/guardian may verbally report signs and symptoms of AD with onset at least 3 months prior).
4. IGA score of 2 to 3 at the screening and baseline visits.
5. %BSA (excluding the scalp) with AD involvement of 3% to 20% at the screening and baseline visits.
6. For children aged 6 years to < 12 years, baseline itch NRS score ≥ 4 (see Section 8.2.7).
Note: Participants who are aged 6 years to < 12 years must record Itch NRS scores for at least 4 of the 7 days immediately prior to the Day 1/baseline visit.
7. Participants/guardians who agree to discontinue all agents used by the participant to treat AD from the screening visit through the final safety follow-up visit.
8. For participants who sign photography consent, at least 1 target lesion that measures at least 5 cm² at the screening and baseline visits. The target lesion must be representative of the participant's disease state but not located on the hands, feet, or genitalia.

9. For sexually active participants, willingness to take appropriate contraceptive measures (see [Appendix A](#)) to avoid pregnancy or fathering a child for the duration of study participation with the exception of male and female participants who are prepubescent.

Note: Female participants who have reached menarche must have a negative urine pregnancy test at the screening and baseline visits before the first application of study cream on Day 1. They must also take appropriate precautions to avoid pregnancy from the screening visit through the safety follow-up visit.

10. Ability to comprehend and willingness to sign an ICF or written informed consent of the parent(s) or legal guardian and a verbal or written assent from the participant when possible.

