8.2.7. Itch Numerical Rating Scale

[figure not shown]
The Itch NRS will be administered based on the participant's age (at the time of consent), as follows:

[figure not shown]
- For participants \geq 6 years of age, collect the Itch NRS. Baseline itch (defined as the average of the 7 days directly before Day 1, with Itch NRS values available for at least 4 of the 7 days) must be \geq 4 on NRS.
- For participants < 6 years of age, do not collect the Itch NRS.

The Itch NRS is a daily participant-reported measure (24-hour recall) of the worst level of itch intensity ([Pruritus Resources](#)). Participants will be asked to rate the itch severity of their AD by selecting a number from 0 (no itch) to 10 (worst imaginable itch) that best describes their worst level of itching in the past 24 hours as outlined in the SoA (see [Table 3](#)). Participants will be issued a diary in which to record itch severity. The participants will be instructed to complete the diary each night beginning on the day of screening through the last application of study cream during the VC period. This is particularly important for the 7 days immediately prior to the Day 1/baseline, Week 2, Week 4, and Week 8 visits; therefore, Itch NRS scores are required for at least 4 of those 7 days during each of these 4 weeks to allow evaluation of participant eligibility and the Itch NRS endpoints. Detailed directions for the administration of a diary will be provided in the Study Reference Manual.

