10.4.2. Secondary Analyses

Secondary efficacy analyses will be conducted on the ITT population. If the primary objective is achieved, the statistical comparisons for key secondary endpoints will be tested with the procedures specified in [Figure 9](#).

The Itch NRS score for baseline will be determined by averaging the 7 daily NRS scores directly before Day 1 (Day -7 to Day -1). The by-visit Itch NRS score for postbaseline visits will be determined by averaging the 7 daily NRS scores directly before the visit day. If 4 or more daily scores are missing (out of the 7), the Itch NRS score at the visit will be set to missing. The same nonresponder imputation method as specified in the primary analysis will be used to handle missing Week 8 itch data, and the logistic regression described in Section 10.4.1 will be applied to compare each ruxolitinib cream group and the vehicle cream group for the key secondary endpoint of Itch NRS score responses at Week 8.

For the key secondary endpoints of Itch NRS score responses on Day 7 (Week 1) and Day 3, all participants who are missing Day 7 and/or Day 3 daily Itch NRS scores will be imputed using multiple imputation by fully conditional specification method. The variables to be included in the imputation regression model are treatment group, stratification factor, baseline itch score, and postbaseline daily itch score on Day 1 to Day 7. The details of the multiple imputation, including number of imputations and seed number, will be specified in the SAP. After the missing values have been imputed, the binary variable for the ≥ 4 -point improvement in Itch NRS score on Day 7 and Day 3 will be derived. The logistic regression specified in Section 10.4.1 will be applied to each imputed dataset, and then the results will be combined for the inference.

All other secondary [REDACTED] efficacy variables will be summarized using descriptive statistics. For categorical measurements, summary statistics will include sample size, frequency, and percentages. Similar logistic regression models as specified in the primary and key secondary analysis will be used if applicable. For continuous measurements, summary statistics will include sample size, mean, median, standard deviation, standard error of the mean, minimum, and maximum. Continuous efficacy endpoints, including the actual measurement, change from baseline, and percentage change from baseline, may also be analyzed by the mixed-effect model with repeat measurement.

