APPENDIX F. PROTOCOL AMENDMENT SUMMARY OF CHANGES

Document	Date
Amendment 1	06 MAY 2021
Amendment 2	02 AUG 2021
Amendment 3	19 AUG 2021
Amendment 4	06 APR 2022
Amendment 5	29 JUL 2022
Amendment 6	22 FEB 2023

Amendment 6 (22 FEB 2023)

Overall Rationale for the Amendment:

The primary purpose of the amendment is to add 2 key secondary endpoints. Details of these and other minor changes are listed below.

1. Section 1, Protocol Summary (Table 1: Primary and Key Secondary Objectives and Endpoints); Section 3, Objectives and Endpoints (Table 7: Objectives and Endpoints); Section 10.3, Level of Significance; Section 10.4.2, Secondary Analyses

Description of change: The proportion of participants with a \geq 4-point improvement in Itch NRS score from baseline to Day 7 (Week 1) and from baseline to Day 3 were added as key secondary endpoints. Statistical details were also added for these 2 additional key secondary endpoints.

Rationale for change: To include an alpha-controlled assessment of early itch reduction with ruxolitinib cream.

2. Section 1, Protocol Summary (Table 2: Key Study Design Elements)

Description of change: [REDACTED], MD, was added as the coordinating principal investigator.

Rationale for change: A coordinating principal investigator is required.

3. Section 10.2, Populations for Analysis

Description of change: Overall application compliance, which is an example of important protocol deviations that may significantly affect the primary analysis as part of the definition of the PP population, was modified from less than 60% to less than 80%.

Rationale for change: [REDACTED]

4. Incorporation of administrative changes. Other regulatory guidance and administrative changes have been incorporated throughout the Protocol and are noted in the redline version of the amendment.

Amendment 5 (29 JUL 2022)

Overall Rationale for the Amendment:

The primary purpose of the amendment is to increase the overall sample size. The changes have no safety implications for this population of participants. Details of these and other minor changes are listed below.

1. Section 1, Protocol Summary (Table 2: Key Study Design Elements; Figure 1: Study Design Schema); Section 10.1, Sample Size Determination

Description of change: The sample size for this trial is being increased from 250 to 315 participants.

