7.3. Analysis of the Key Secondary Efficacy Parameters

7.3.1. Key Secondary Efficacy Measures

7.3.1.1. Itch Numerical Rating Scale Score

The Itch NRS is a once-daily patient-reported measure of itch intensity assessed using an 11-point scale (0 = no itch to 10 = worst imaginable itch). Participants aged 6 years or older will be asked to record their highest (worst) level of itch in the evening over the 24-hour recall period.

The Itch NRS score for baseline will be determined by averaging the 7 daily NRS scores directly before Day 1 (Day -7 to Day -1) for all the by-visit summaries. The by-visit Itch NRS score for postbaseline visits will be determined by averaging the 7 daily NRS scores directly before the visit day. If 4 or more daily scores are missing (out of the 7), the Itch NRS score at the visit will be set to missing. For all daily itch related analyses, including time to achieve Itch NRS score improvement of at least 2 or 4 points analyses, baseline will be defined as the last available Itch NRS score during the week prior to Day 1 (Day -7 to Day -1).

The proportion of participants with a clinically relevant change in itch, defined as a ≥ 4 -point improvement in by-visit or daily Itch NRS score from baseline, will be summarized by treatment group for participants with baseline Itch NRS score ≥ 4 .

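### Does the SAP's last-single-score baseline for the Day 7 and Day 3 itch tests conflict with the protocol's 7-day mean in a way that needs a change?

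*SAP*

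**What the plan says.** **Protocol.** Section 10.4.2 states "The Itch NRS score for baseline will be determined by averaging the 7 daily NRS scores directly before Day 1", with no words limiting this to particular endpoints. The same paragraph goes on to visit scores, the rule for missing diary days and the Week 8 responder test. A separate paragraph covers the Day 7 and Day 3 endpoints. It works with daily scores and refers to the baseline only in passing: "The variables to be included in the imputation regression model are treatment group, stratification factor, baseline itch score". Elsewhere the mean serves as the entry rule, in Table 3 ("baseline itch (defined as the average of at least 4 of the 7 days directly before Day 1"), in section 8.2.7 ("Baseline itch (defined as the average of the 7 days directly before Day 1") and, by reference to 8.2.7, in Inclusion Criterion 6 ("For children aged 6 years to < 12 years, baseline itch NRS score" of at least 4). Amendment 6 added the two early endpoints; its stated reason was "To include an alpha-controlled assessment of early itch reduction with ruxolitinib cream".

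**SAP.** Section 7.3.1.1 restricts the mean to visit-level work ("scores directly before Day 1 (Day -7 to Day -1) for all the by-visit summaries"). For all analyses of daily itch, "baseline will be defined as the last available Itch NRS score during the week prior to Day 1 (Day -7 to Day -1"). Section 7.3.2 derives Day 7 and Day 3 response by reference to 7.3.1.1. In Appendix A, Table 2.3.6 and Figure 4.3.6 take as their population the ITT children whose daily baseline is ≥ 4. The general rule in SAP 4.1.3 is the last nonmissing value up to the day of first application. SAP 11.1 reports no changes to protocol-defined analyses.

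**The concern.** A reader of the protocol alone would probably expect the 7-day mean for every itch endpoint, because no other itch baseline is given there. The SAP uses something else for four tests under familywise error control and does not list it as a change. Version lag is no explanation, since SAP 2.1 says the SAP was written against Amendment 6, which added these endpoints and revised protocol 10.4.2.

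The baseline does two jobs. It fixes the point from which a 4-point improvement is measured, and it decides who is in the analysis. A child aged 6 or older enters on a mean of at least 4. If that child's last score before Day 1 is below 4, the child stays in the Week 8 itch test but leaves the Day 7 and Day 3 tests. Under SAP 3.2, Day 3 is tested only if both Day 7 hypotheses are rejected, so the choice could also decide whether Day 3 is tested at all.

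**Working it through.** **1. Can the definitions disagree for one child?** Improvement is baseline minus the later score; a responder needs ≥ 4.

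| Scores, Day -7 to Day -1 | Mean | Last | Later score | Improvement from mean | Improvement from last |
|---|---|---|---|---|---|
| 5,5,5,5,5,5,7 | 37/7 = 5.29 | 7 | 3 (Day 3) | 2.29, nonresponder | 4, responder |
| 7,7,7,7,7,7,4 | 46/7 = 6.57 | 4 | 2 (Day 7) | 4.57, responder | 2, nonresponder |
| 5,5,5,4,4,4,3 | 30/7 = 4.29 | 3 | – | in the set | out of the set |

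They can, and in either direction. With the minimum of 4 diary entries out of 7, the last available score can be as old as Day -4.

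**2. Do the documents contradict each other?**

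- The protocol's averaging sentence opens a paragraph whose remaining content is visit scores and Week 8.
- The Day 7/Day 3 paragraph uses daily scores, repeats no averaging rule and defines no daily baseline.
- Table 3 and section 8.2.7 tie the mean to eligibility. Section 8.2.7 asks for 4 of 7 diary days only before Day 1 and Weeks 2, 4 and 8, which are the visits with averaged scores.
- Section 10.4 describes itself as a summary.
- The SAP's daily rule is close to its own default in 4.1.3, confined to Day -7 to Day -1. Within the SAP, the 7-day mean is the special case.

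Filling a gap is therefore a reasonable reading, although the protocol's words do not exclude the other one.

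**3. Does an analyst have one answer?** Yes. SAP 7.3.1.1, 7.3.2, Table 2.3.6 and Figure 4.3.6 all lead to the same baseline and the same set. The imputation code in 7.3.2 has a variable named base with no definition. In a model of daily scores on Days 1 to 7, the natural reading is the daily baseline from 7.3.1.1.

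**4. Is the comparison valid?** Baseline scores precede treatment and the rule is the same in every arm. Restricting to last score ≥ 4 is a restriction on a pre-treatment variable. Each hypothesis keeps one prespecified test.

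**5. Does any stated figure move?** No power is stated for Day 7 or Day 3. The itch power in Appendix F (Amendment 5) is for Week 8, where both documents use the mean. With 180 children at 2:2:1 (72/72/36) and two-sided alpha 0.025:

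- 52% v 16%: 93.6% by exact Fisher, 94.5% by the normal formula; stated as > 90%.
- 42% v 16%: 67.7% and 70.0%; stated as 70%.

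These stand whichever daily baseline is used.

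**6. Illustration of the treatment contrast.** The documents give neither a day-to-day SD nor early response rates, so these inputs are assumed: child means with average 6.3 and SD 1.6, day SD 1.5, improvement SD 2.0, integer scores 0 to 10, complete diaries, entry mean ≥ 4. Mean-baseline rates for 1.5%, 0.75% and vehicle are set to 52/42/16% (A, the Week 8 planning rates) or half of that (B).

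| | Difference from vehicle, mean baseline | Difference from vehicle, last score |
|---|---|---|
| A, 1.5% | 36.0 points | about 35.5 |
| A, 0.75% | 26.0 | about 26.5 |
| B, 1.5% | 18.0 | about 21 |
| B, 0.75% | 13.0 | about 15.5 |

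Response rises in every arm with the last score (vehicle in A from 16% to about 24%), so the contrast moves far less than the arm rates. About 5.8% of children leave the set. That alone hardly matters: in A the mean-baseline rates among those who remain are 52.1% (1.5%) and 16.1% (vehicle).

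**The case for a change.** The strongest case for acting is textual. The protocol's sentence carries no qualifier, and the words confining the mean to visit summaries appear only in the SAP. Protocol 10.4.2 hands the imputation details to the SAP but not the baseline. A responder definition in an alpha-controlled family is a poor place for an unannounced difference, and the remedy looks cheap: align the documents and prespecify the other baseline as a sensitivity analysis.

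Part of this stands. SAP 11.1 would have been better with a line recording the daily baseline and the reason for it, and the last score is a noisier anchor than a mean.

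The rest does not carry to a change. The single score compares one day with one day; the mean matches the entry rule and the Week 8 test but sets seven days against one. That is a fair trade-off with no clear winner. Simulated power also gives no guide: under the assumed rates, the chance of reaching Day 3 with the single score changes by -9.1 to -1.5 points in scenario A and by +0.6 to +6.9 in scenario B. Rewording protocol 10.4.2 would require an amendment, which protocol 11.1 sends to health authorities and ethics review, to restate a rule the SAP already makes plain. A 7-day-mean analysis of Day 7 and Day 3 is harmless but optional.

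**Conclusion.** No change to the plan follows. The wording difference is real but amounts to a protocol summary that never defines a daily itch baseline and a SAP that supplies one. The SAP rule is prespecified, unambiguous, based on pre-treatment data and carried through text and outputs alike, so following it gives sound tests of H13, H23, H14 and H24.

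Individual children can be classified differently under the two definitions, as the worked examples show without any assumptions. How often that would happen cannot be known from the documents; the simulated figures rest on assumed variability and response rates, omit covariates and imputation, and serve only to show that the treatment contrast is much steadier than the arm rates. The primary endpoint and the Week 8 itch endpoint are unaffected, and the early itch tests are reached only after all four Step 1 rejections.

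The one residue is clerical: SAP 11.1 does not mention the daily baseline. The conclusion assumes that base in the imputation code is the daily baseline of SAP 7.3.1.1, as its context implies.

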7.3.2. Key Secondary Efficacy Analysis

Key secondary efficacy analyses will be conducted in the ITT population in the VC period. If the primary objective is achieved, the statistical comparisons for key secondary endpoints will be tested with the procedures specified in Section 3.2.

The same nonresponder imputation method as specified in the primary analysis will be used to handle missing Week 8 itch data, and the logistic regression described in Section 7.2.2 will be applied to compare each ruxolitinib cream group and the vehicle cream group for the key secondary endpoint of ≥ 4 -point improvement in Itch NRS score response at Week 8.

For the key secondary endpoints of Itch NRS score responses on Day 7 (Week 1) and Day 3, all participants who are missing Day 7 and/or Day 3 daily Itch NRS scores will be imputed using multiple imputation by fully conditional specification method. The variables to be included in the imputation regression model are treatment group, stratification factor, baseline itch score, and postbaseline daily itch score on Day 1 to Day 7. The corresponding binary response on Day 7 and Day 3 will be derived for each of the imputed datasets per the definition in Section 7.3.1.1. The logistic regression specified in Section 7.2.2 will be applied to each imputed dataset and then the results will be combined for the inference using Rubin's rule.

The following sample SAS code will be used for the MI:

```
proc mi data=mi_wide seed=18424 n impute=30 out=impute_itch;
  class trt01p strat1 strat2;
  var trt01p strat1 strat2 base avald1 avald2 avald3 avald4 avald5
  avald6 avald7;
  fcs regpmm nbiter=30;
run;
```

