10.2. Populations for Analysis

[Table 12](#) presents the populations for analysis.

Table 12: Populations for Analysis

Population	Description
ITT	The ITT population includes all randomized participants. Treatment groups for this population will be defined according to the treatment assignment at randomization.
PP	The PP population includes randomized participants who are considered to be sufficiently compliant with the Protocol. In general, the following are important protocol deviations that may significantly affect the primary analysis: Missing data for the primary endpoint Overall application compliance less than 80% during the VC period Participants with one or more such deviations will be excluded from the PP population. In addition, important protocol deviations related to inclusion/exclusion criteria, discontinuation criteria, and use of prohibited concomitant medications will be reviewed. Decisions as to whether any of these deviations warrant exclusion from the PP population will be made prior to unblinding.
Safety	The safety evaluable population includes all participants who applied study cream at least once. Treatment groups for this population will be determined according to the actual treatment the participant received on Day 1.
LTS evaluable	All analyses for the LTS period will be conducted with the LTS evaluable population, which includes all participants who applied study cream at least once during the LTS period.
	[REDACTED]

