Rationale for change: The evaluable population for the key secondary endpoint (proportion of participants with a \geq 4-point improvement in Itch NRS score from baseline to Week 8) requires participants 6 years of age or older who have nonmissing baseline Itch NRS scores. It was discovered that this subgroup was under-enrolled at a time when the overall enrollment was close to final. Based on the enrollment status on 14 JUL 2022, among 255 participants screened, approximately 116 participants were qualified in that subgroup. To ensure enough power for this key secondary endpoint, at least 180 participants are required in this subgroup, and to achieve that the overall population will be increased from 250 to 315.

The sample size calculation of 180 in this subgroup is based on the results from the 2 pivotal studies, INCB 18424-303 and INCB 18424-304, in which the response rate for the key secondary endpoint at Week 8 is assumed to be 52% and 42% for the active arms (ruxolitinib 1.5% cream BID and ruxolitinib 0.75% cream BID, respectively) versus 16% for vehicle cream BID. Using a 2-sided alpha of 0.025, the sample size will have $> 90\%$ power to detect a difference between ruxolitinib 1.5% cream BID versus vehicle cream BID and 70% power to detect a difference between ruxolitinib 0.75% cream BID versus vehicle cream. In addition to providing adequate power for all efficacy variables, the sample size increase is also providing a larger database for safety evaluation.

2. Section 1, Protocol Summary (Table 3: Schedule of Activities: Vehicle-Controlled Period); Section 5.1, Inclusion Criteria (Inclusion Criterion 8); Section 8.2.3, Target Lesion Identification; Section 8.2.4, Photography

Description of change: Instructions were added such that only participants who are participating in photography are required to identify and measure target lesions at the screening and baseline visits. For participants not participating in photography, the identification and measurement of target lesions are optional.

Rationale for change: Clarification was added that only participants who are participating in photography are required to identify and measure target lesions.

3. Section 5.1, Inclusion Criteria (Inclusion Criterion 6); Section 8.2.7, Itch Numerical Rating Scale

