2.3.1	Summary and Analysis of Participants Achieving \geq 4-Point Improvement in Itch NRS Score in the VC Period by Visit	ITT with baseline Itch NRS Score \geq 4	
2.3.3	Summary and Analysis of Time to \geq 2-Point Improvement in Itch NRS Score in the VC Period	ITT with daily baseline Itch NRS Score \geq 2	
2.3.4	Summary and Analysis of Time to \geq 4-Point Improvement in Itch NRS Score in the VC Period	ITT with daily baseline Itch NRS Score \geq 4	
2.3.6	Summary and Analysis of Participants Achieving \geq 4-Point Improvement in Itch NRS Score from Day 1 to Day 7	ITT with daily baseline Itch NRS Score \geq 4	

Table No.	Title	Population	Standard

Table No.	Title	Population	Standard
Exposure, Adverse Events, Laboratory, and Vital Signs			

Exposure			
3.1.1.1	Summary of Exposure During the VC Period	Safety	X
3.1.1.2	Summary of Exposure During the LTS Period	LTS Evaluable	X
3.1.1.3	Summary of Exposure From Baseline to Week 52	Safety	X
3.1.2	Summary of Study Drug Compliance During the VC Period	Safety	X
Adverse Events			
3.2.1.1.1	Overall Summary of Treatment-Emergent Adverse Events in the VC Period	Safety	X
3.2.1.1.2	Overall Summary of Treatment-Emergent Adverse Events by Age Group in the VC Period	Safety	X
3.2.1.1.3	Overall Summary of Treatment-Emergent Adverse Events in the LTS Period	LTS Evaluable	X
3.2.1.1.4	Overall Summary of Treatment-Emergent Adverse Events for Participants Who Applied Ruxolitinib Cream Throughout the Study (Baseline to Week 52)	Safety	X
3.2.2.1.1	Summary of Treatment-Emergent Adverse Events by MedDRA System Organ Class and Preferred Term in the VC Period	Safety	X

Table No.	Title	Population	Standard
3.2.2.1.2	Summary of Treatment-Emergent Adverse Events by MedDRA System Organ Class and Preferred Term by Age Group in the VC Period	Safety	X
3.2.2.1.3	Summary of Treatment-Emergent Adverse Events by MedDRA System Organ Class and Preferred Term in the LTS Period	LTS Evaluable	X
3.2.2.1.4	Summary of Treatment-Emergent Adverse Events by MedDRA System Organ Class and Preferred Term for Participants Who Applied Ruxolitinib Cream Throughout the Study (Baseline to Week 52)	Safety	X
3.2.3.1.1	Summary of Treatment-Emergent Adverse Events by MedDRA Preferred Term in Decreasing Order of Frequency in the VC Period	Safety	X
3.2.3.1.2	Summary of Treatment-Emergent Adverse Events by MedDRA Preferred Term in Decreasing Order of Frequency by Age Group in the VC Period	Safety	X

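### The alpha-controlled itch tests are assigned to unrestricted ITT in SAP 7.3.2 and Protocol 10.4.2, but to participants with baseline Itch NRS ≥ 4 in SAP 7.3.1.1 and Appendix A

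*SAP*

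**What the plan says.** **Unrestricted ITT.** The section that defines the tests, SAP 7.3.2, says "Key secondary efficacy analyses will be conducted in the ITT population in the VC period". Protocol 10.4.2 says "Secondary efficacy analyses will be conducted on the ITT population". Protocol 10.2 defines the set: "The ITT population includes all randomized participants".

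**Week 8 missing data.** SAP 7.3.2 adds: "The same nonresponder imputation method as specified in the primary analysis will be used to handle missing Week 8 itch data". SAP 4.1.5 counts a participant with no Week 8 value as a nonresponder.

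**Day 7 and Day 3 missing data.** Both documents use multiple imputation by fully conditional specification. The rule covers everyone without a Day 7 or Day 3 score and sets no limit by age or baseline. The sample PROC MI code in SAP 7.3.2 lists the baseline and the seven daily scores as variables.

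**Who has itch data.** Protocol 8.2.7 says, for participants under 6, "years of age, do not collect the Itch NRS".

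**The restricted set.** SAP 7.3.1.1 says the proportion with at least a 4-point improvement, by visit or daily, "will be summarized by treatment group for participants with baseline Itch NRS score" of at least 4. In Appendix A, Table 2.3.1 (by visit) has the population "ITT with baseline Itch NRS Score" of at least 4. Table 2.3.6 (Day 1 to Day 7) uses ITT with a daily baseline of at least 4. Both tables are titled as summary and analysis. The two baselines differ: SAP 7.3.1.1 uses a 7-day mean for visits and the last available score in that week for daily analyses.

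**The concern.** These six hypotheses are confirmatory. H12 and H22 must both be rejected, along with the two primary hypotheses, before Step 2 opens, so their population also governs whether H13, H23, H14 and H24 are tested at all.

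The population decides who counts as a nonresponder. If SAP 7.3.2 is followed as worded at Week 8, every child under 6 enters the denominator and none can enter the numerator. The resulting difference depends on the age mix recruited. It is also not comparable with the pivotal-study itch rates in Protocol Table 6, whose denominator was ITT participants with baseline Itch NRS of at least 4, and the power in the Amendment 5 rationale does not describe it.

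For Day 7 and Day 3 the children who were never asked are not set to nonresponse. If they are in the imputation dataset, they receive an imputed baseline and imputed daily scores that rest only on treatment group, strata and older children's data.

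**Working it through.** **Inputs**
- Randomised: 315 at 2:2:1, that is 126:126:63 (Protocol 10.1 and Table 2).
- Itch-evaluable: at least 180 (Protocol Appendix F, Amendment 5 rationale), which is 72:72:36 if 2:2:1 holds within the subgroup (assumption).
- Week 8 itch response: 52% (1.5%), 42% (0.75%) and 16% (vehicle); two-sided alpha 0.025 (same rationale).
- Stated power in the 180: > 90% for 1.5% and 70% for 0.75%.

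**Power formula** (pooled-variance normal approximation, z = 2.2414)

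Power = Φ{[d − z·√(p̄(1−p̄)(1/n₁+1/n₂))] / √(p₁(1−p₁)/n₁ + p₂(1−p₂)/n₂)}

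**Step 1: reproduce the plan's figures in the subset (72 v 36)**
- 1.5%: p̄ = (72×0.52 + 36×0.16)/108 = 0.400. Numerator 0.360 − 2.2414×0.1000 = 0.1359; denominator 0.0849; power Φ(1.60) = 94.5%.
- 0.75%: p̄ = (72×0.42 + 36×0.16)/108 = 0.333. Numerator 0.260 − 2.2414×0.0962 = 0.0443; denominator 0.0844; power Φ(0.525) = 70.0%.

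Both stated figures are reproduced. The two-sided Fisher exact test gives 93.6% and 67.7%.

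**Step 2: Week 8 under the literal rule (126 v 63)**

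With evaluable share f = 180/315 = 0.571, each arm's rate is multiplied by f because the other 135 participants count as zero. The shrinkage in the difference is 1 − f = 42.9%.

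| | Subset | Literal ITT with nonresponder imputation |
|---|---|---|
| Rates (1.5% / 0.75% / vehicle) | 52% / 42% / 16% | 29.7% / 24.0% / 9.1% |
| Difference, 1.5% | 36.0 points | 20.6 points |
| Difference, 0.75% | 26.0 points | 14.9 points |
| Odds ratio, 1.5% / 0.75% | 5.69 / 3.80 | 4.20 / 3.14 |
| Power, 1.5% | 94.5% | 86.6% (Fisher 86.0%) |
| Power, 0.75% | 70.0% | 59.6% (Fisher 58.8%) |

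If 60% were evaluable (assumed), the shrinkage would be 40.0% and power about 89% and 63%.

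**Step 3: effect of age adjustment**

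The planned model includes age (2–6 v 7 to < 12 years), which absorbs much of the dilution. The logistic Wald test was simulated with adjustment for age stratum, at 1,500 trials per setting, assuming that one sixth of evaluable children are 6-year-olds in the younger stratum. In one run, subset v literal ITT power was 92.9% v 92.3% (1.5%) and 69.9% v 65.8% (0.75%). A repeat gave 93% v 91% and 68% v 66%. The Monte Carlo standard error near 66% is √(0.66×0.34/1500) = 1.2 points, so the adjusted loss is small.

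**Step 4: Day 7 and Day 3**

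The scaling by f does not apply, because missing scores are imputed rather than set to nonresponse. If the imputation dataset holds all randomised participants, about 135 of 315 (43%) would have no observed baseline and no observed daily score. Because the baseline is in the variable list, the procedure would fill that in too. In the Table 2.3.6 set, every member has an observed daily baseline, so none would be imputed.

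**The case against.** The best reply is that the SAP as a whole points to the subset. SAP 7.3.1.1 sits under the key secondary measures and names the restriction. SAP 7.3.2 refers back to it for the Day 7 and Day 3 response. Tables 2.3.1 and 2.3.6 cover the analysis as well as the summary, and no visible itch-responder output uses unrestricted ITT. The pivotal studies used the same denominator. On this view ITT only means analysed as randomised.

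As evidence of intent, that stands. A reader might infer that the sponsor means to count children under 6 as itch nonresponders; the documents do not support that. But the intent has to be pieced together. SAP 7.3.1.1 speaks of summarising, the cross-reference covers only Day 7 and Day 3, and Appendix A calls its own lists guidelines. The section that specifies the Week 8 test and its missing-data rule says ITT without qualification.

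The imputation objection also has force: the code is labelled as a sample and its input dataset is not defined. The Day 7 and Day 3 point is therefore what the wording permits, not what will certainly be run.

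Four further inferences should not be drawn:
- **A third population definition.** Amendment 5 says the evaluable population "requires participants 6 years of age or older who have nonmissing baseline Itch NRS scores". That is a change-log rationale, and inclusion criterion 6 (baseline itch of at least 4 from age 6) makes it nearly the same set as Appendix A's.
- **A larger dilution from the observed share.** Taking 116/255 would give 54.5% shrinkage, but that is a share of participants screened by 14 July 2022, before the increase meant to reach 180.
- **An undeclared departure in SAP 11.1.** Protocol 10.4 leaves the description of analysis populations to the SAP.
- **A material effect from children aged 6 or older without a valid baseline.** The documents give no figure, and criterion 6 should make such children rare.

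**Conclusion.** The conflict is real and should be resolved in SAP 7.3.2. At Week 8 the literal rule shrinks the differences by 43%. Power for 1.5% and 0.75% falls to about 87% and 60% unadjusted, but by only about 2 points or less and 2 to 4 points respectively with age adjustment. The main harm is therefore to the estimate and its interpretation, with a secondary effect on power.

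A reader might extend nonresponder imputation and the 43% to all six itch hypotheses. The documents do not support this: both apply to H12 and H22 only. For H13, H23, H14 and H24 the defect is an imputation with no stated age or baseline limit, and no size can be put on it from the documents.

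The figures assume the plan's response rates, 180 of 315 evaluable, 2:2:1 within the subgroup, and that the 180 closely matches the baseline ≥ 4 set.

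**What to change.** In SAP 7.3.2, replace the unqualified ITT statement for the itch endpoints with the populations already named in Appendix A:
- H12 and H22: ITT participants with by-visit (7-day mean) baseline Itch NRS of at least 4 (Table 2.3.1).
- H13, H23, H14 and H24: ITT participants with daily baseline Itch NRS of at least 4 (Table 2.3.6).

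State that nonresponder imputation applies only to members of the Week 8 set. Restrict the PROC MI input dataset to the Table 2.3.6 set before imputation.

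The cost is a few lines of text and one data filter, before unblinding. The downside is that the itch result is labelled as a subset of ITT. A note in SAP 11.1, and a supportive analysis counting children aged 6 or older without a valid baseline as nonresponders, are optional.
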